- Treatment Plan: Treatment will be initiated with REVLIMID® at 25 mg/day taken in the morning. Dose adjustments may be made to alleviate toxicities. Patients will be assessed for treatment response each 28-day cycle for the first 2 28-day cycles, then every 2 28-day cycles for a total treatment time of one year. At one year, those patients that are maintaining tumor response to REVLIMID® treatment and wish to continue these treatments will enter into the "Extended Therapy" phase. These patients may continue with extended drug therapy through the RevAssist® program see Appendix 1, in 28-day cycles with treatment response and routine tumor assessment every three months. The Celgene Corporation will supply REVLIMID® as 5 mg and 25 mg capsules and will be dispensed by the designated investigational pharmacy. REVLIMID that is provided through the RevAssist program will be supplied as 5 mg, 10 mg, 15 mg and 25 mg capsules.

Treatment will be continued, past each response assessment point (starting with the second 28-day cycle), as long as there is no evidence of disease progression at an equal or greater rate than documented for the baseline year prior to initiation of treatment. Alternatively, unacceptable toxicity will result in a dose reduction or termination of REVLIMID® therapy, as per strict criteria.

Statistical Evaluations: A two-stage design will be used, as described by Gehan (4), which entails the evaluation of 14 patients to determine whether there is at least one patient responsive to this treatment. Would no responders be found within 4 28-day cycles after initiating each of the 14 patients on the study drug, the study will end at that time. In the presence of at least one responder, the trial is planned to continue, accruing an additional 11 patients or sufficient patients to determine a 95% confidence interval for the true response rate. Thus, a total of 14 patients will be enrolled if there are no responders; however, up to 25 patients will be enrolled if there are responders in the initial group. Response rates of 65% have been noted in prior studies using the parent compound, thalidomide (1). Based on such activity, we anticipate that the probability of observing 'no responses' for this treatment regimen in 14 subjects is less than 4.0 x 10⁻⁷. In essence, there is very low probability that this study will not move into the second phase given the levels of tumor activity reported previously for this treatment.

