1.7.4 Studies during the "Extended Therapy" phase: The following studies are obtained after the one-year protocol has concluded and the patient is maintaining a clinical response to REVLIMID® therapy and elects to continue to receive this drug. Note that these studies are performed as "standard-of-care" assessments that are appropriate for oncologic follow-up:

Tumor Assessment (obtained at physician visits every 3 months): Tumor markers: Thyroglobulin Panel (TG & anti-TG Ab), TSH, free T4. Angiogenic Markers: Not done. Radiological Studies: CT (without contrast for lung; otherwise with contrast) of evaluable disease.

Toxicity Monitoring (obtained every month while taking REVLIMID®): CBC with differential/platelet count every 4 weeks.

FCBP with regular or no menstruation must have a pregnancy test every 28 days while on therapy (including breaks in therapy); at discontinuation of lenalidomide and at 30 Days +/- 2 days post the last dose of lenalidomide. Females with irregular menstruation must have a pregnar every 14 days while on therapy (including breaks in therapy), at discontinuation of lenalidomide and at Day 14 and Day 28 post the last dose of lenalidomide (see Appendix F: Risks of Fetal Exposure, Pregnancy Testing Guidelines and Acceptable Birth Control Methods).

Additional standard assessments (obtained at physician visits every 3 months): biochemistry panel and physical examination.

- Outpatient Visits: Patients will report to the University of Kentucky Clinical Research Organization (UKCRO) for outpatient evaluations by the principal investigator and UKCRO nursing staff at: time of initial enrollment, at the start of every 28 day cycle and for a final visit.
 - 1.8.1 Study Duration: Each patient will continue on study for 12 28-day cycles or until there is evidence of disease progression (or patient withdraws from study), whichever is sooner.
 - 1.8.2 Final Visit: Should any patient terminate participation at any time, either out of choice, disease progression, or significant toxicity, there will be a final outpatient visit. Toxicity assessment will be done approximately 30 days after last dose of study drug.

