1.8.3... Extended Therapy phase: Lenalidomide (Revlimid®) will be provided to research subjects for the duration the extened phase participation in this trial at no charge to them or their insurance providers. Lenalidomide will be provided in accordance with the RevAssist® program. Per standard RevAssist® requirements all physicians who prescribe lenalidomide for research subjects enrolled into this trial, and all research subjects enrolled into this trial, must be registered in and must comply with all requirements of Celgene's RevAssist® program. Prescriptions must be filled within 7 days. Only enough lenalidomide for one cycle of therapy will be supplied to the patient each cycle.

Patients will have a CBC prior to each new cycle of Revlimid®. Standard-of-care clinical visits with the principal investigator will take place every 3 months as long as the patient is participating in the Extended Therapy phase.

1.9 Response Criteria:

- 1.9.1 Complete Response (CR): Disappearance of all radiological and clinical evidence of tumor. The patient must be free of all tumor related symptoms for at least 4 weeks.
- 1.9.2 Partial Response (PR): 30% or greater decrease in the sum of the longest diameter of all measured lesions (or alternatively, ≥30% reduction of calculated tumor volumes) for at least 4 weeks.
- 1.9.3 Minor Response (MR): For tumors with a documented rate of progression (calculated as either the linear slope of calculated tumor volumes vs. time for the immediate year prior to initiating this study or as the slope of the logarithm of tumor volumes vs. time over the same interval), a decrease in the rate of progression by ≥50%.
- 1.9.4 Stable Disease (SD): No change or <30% decrease in the tumor volume (calculated as in 1.9.2) for at least 4 weeks.
- 1.9.5 Progressive disease (PD): Less than a 50% reduction in the rate of progression (see 1.9.3), an increase of >25% in the size of any measured lesion, or the appearance of new metastatic lesions.

Table 1: Schedule of Study Assessments

	Screening	Cycle	Cycle	Cycle	Cycle	Cycle	Cycle	Cycle	Cycle ,	Cycle	Cycle	ಲ	Cycle 12	Extension Phase	Extension Phase:	Extended Therapy
Procedure	prior to initiating	. H	79	т	খ	ŧn	9	r-	\$	٥,	2	Ħ	or Endin		Every 1 month	Phase: Every 3
	therapy												g Study			months
Complete medical history (prior treatment),	×															
Physical examination Kamofsky (clinic visit)	×	×	×	×	×	×	×	×	×	×	×	×	×			×

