5.0 Investigational Plan

5.1 Patient Eligibility:

5.1.1 Inclusion Criteria:

- 1) Histological confirmation of follicular, papillary, insular, or Hürthle-cell thyroid carcinoma. Histologic slides and/or tissue blocks must have been reviewed at the University of Kentucky Medical Center.
- 2) Patients must have progressive, unresectable, distantly metastatic tumor, which does not concentrate radioactive iodine. Alternatively, follicular or papillary thyroid carcinoma patients with distant tumor burdens which have not sufficiently responded to more than 800 mCi I-131 cumulative therapy and are progressive (criteria #4) may be appropriate for inclusion.
 - 3) No systemic chemotherapy agents within 4 weeks of initiation of therapy.
- 4) Patients must have 2 consecutive radiographic evaluations demonstrating a cumulative 30% increase in tumor volume over a time period of one year or less.
- 5) Patient must be over the age of 18 years with the ability to understand and willing to sign an informed consent.
- 6) Females of childbearing potential (FCBP)[†] must have a negative serum or urine pregnancy test with a sensitivity of at least 50 mIU/mL within 10 14 days prior to and again within 24 hours of starting lenalidomide and must either commit to continued abstinence from heterosexual intercourse or begin TWO acceptable methods of birth

control, one highly effective method and one additional effective method AT THE SAME TIME, at least 28 days before she starts taking lenalidomide. FCBP must also agree to ongoing pregnancy testing. Men must agree to use a latex condom during sexual contact with a FCBP even if they have had a successful vasectomy. All patients must be counseled at a minimum of every 28 days about pregnancy precautions and risks of fetal exposure. See Appendix F: Risks of Fetal Exposure, Pregnancy Testing Guidelines and Acceptable Birth Control Methods, AND also Appendix G: Education and Counseling Guidance Document.

- 7) Karnofsky performance status ≥70 %.
- 8) Baseline Laboratory Studies: Absolute neutrophil count (ANC) >1000/mm³; platelet count \geq 100 K/mm³; Creatinine \leq 2 mg/dL, and transaminase levels (AST/SGOT, ALT/SGPT) \leq 2 x ULN (or \leq 5 x ULN if hepatic metastases are present).
- 9) Disease free of other prior malignancies for ≥ 5 years, with the exception of currently treated basal cell/squamous cell carcinoma of the skin or "in-situ" carcinoma of the cervix or breast.

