- 10) TSH (thyrotropin) levels must be suppressed with sufficient levothyroxine to be kept beneath the normal range of the assay.

5.1.2 Exclusion Criteria:

- 1) Patients may not have had prior REVLIMID® therapy.
- 2) No serious concomitant medical or psychiatric illness that might interfere with informed consent or conduct of the study, including active infections that are not controlled with medication.
 - 3) Patients must not be pregnant or breastfeeding.
 - 4) Use of any other experimental drug or therapy within 28 days of baseline.
 - 5) Known hypersensitivity to thalidomide.
- 6) The development of erythema nodosum characterized by a desquamating rash while taking thalidomide or similar drugs.
- 7) Any condition, including the presence of laboratory abnormalities, which places the subject at unacceptable risk if he/she were to participate in the study or confounds the ability to interpret data from the study.

[†] A female of childbearing potential is a sexually mature woman who: 1) has not undergone a hysterectomy or bilateral cophorectomy; or 2) has not been naturally postmenopausal for at least 24 consecutive months (i.e., has had menses at any time in the preceding 24 consecutive months).

- 8) Concurrent use of other anti-cancer agents or treatments, with the exception of thyrotropin-suppression by levothyroxine.
- 9) All subjects with central nervous system involvement, with the exception of those subjects whose central nervous system metastases have been treated with either radiotherapy and/or surgery and remains asymptomatic with no evidence of active central nervous system disease (verified by CT scan or MRI) for at least 6 months.
 - 10) Patients known to be positive for HIV or infectious hepatitis, type A, B, or C.
- 11) Patients with medullary or anaplastic thyroid carcinomas are excluded. Patients whose disease is limited to bone metastases are excluded.

5.2 Treatment Plan:

- 5.2.1 Therapy is administered on an outpatient basis.
- 5.2.2 Treatment Drugs: Patients will receive the study drug as long as there is no evidence of disease progression (as defined in section 9.0 Response Criteria) or unacceptable toxicity.
- 5.2.2.1 Patients must continue to take levothyroxine at a dose sufficient to suppress the TSH level ≤0.1 while avoiding significant thyrotoxicosis.

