6.0 Pre-Treatment Evaluation: (Patient must sign IRB consent form)

6.1 Basic Data: Physical examination and medical history; Laboratory tests (urinalysis, electrolytes, BUN, creatinine, hepatic enzymes, bilirubin, ionized calcium, phosphorus, glucose, albumin, PT, aPTT), baseline electrocardiogram.

6.2 Tumor Assessment:

- 6.2.1 Tumor markers: thyroglobulin panel (thyroglobulin & anti-thyroglobulin antibody), TSH, free T4.
- Radiological Studies: Patients must have at least one year of radiographic evidence of tumor progression with at least 2 separate x-ray studies (preferably CT or MR scans) able to define tumor volume, or similar radiographic evidence over a shorter period of time delineating greater than 30% increased tumor volume (to permit comparison of rate of tumor progression with each patient as their own control). A baseline radiological evaluation of tumor volume must be obtained within one week prior to initiating REVLIMID®.
- 6.2.3 Tumor Volume Assessment Methodology: Volumetric tissue measurements are well established for both MR and CT scans which are generally performed on an independent imaging work station (38-41). A Siemen's Magic View PACS workstation will be used to perform volumetric measurements on metastatic tumor(s) utilizing software VB 32 release B updated on 2/2000 written by Sun Microsystems. An irregular ROI (region of interest) curve will be traced around the tumor(s) on dual high-resolution 1024 x 1024 matrix monitors. All tracings CONFIDENTIAL

will be stored on CD-ROM for reproducibility as well as visual inspection of tumor(s) size change by superimposing the most recent study on the prior study.

CT images will be obtained with a 3 mm thick beam incremented at 1 mm intervals. The 3 mm thickness is chosen to reduce the graininess due to quantu mottling with a 1.5 mm thick beam (smallest available slice). The calculated surface area of each 1 mm thin slice contained in the irregular shaped ROI will be added to the other slices to yield a three dimensional volume. Depending on whether the evaluable disease sites require oral or IV contrast for imaging, the CT scan will be either with or without such contrast material. All CT scans will be performed on a Siemen's Somatom CT scanner.

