- 9.1.5 Progressive disease (PD): Less than a 50% reduction in the rate of progression (see 9.1.3), an increase of >20% in the size of target lesions, or the appearance of new metastatic lesions.

Figure 4. Overall responses for all possible combinations of tumor responses in target and non-target lesions with or without the appearance of new lesions* (Adapted from Therasse P, Arbuck SG, Eisenhauer EA, Wanders J, Kaplan RS, Rubinstein L, Verweij J, Van Glabbeke M, van Oosterom AT, Christian MC, Gwyther SG 2000 New guidelines to evaluate the response to treatment in solid tumors. European Organization for Research and Treatment of Cancer, National Cancer Institute of the United States, National Cancer Institute of Canada. J Natl Cancer Inst 92:205-16)

Target lesions	Non-target lesions	New lesions	Overall response
CR.	CR	No	CR
CR.	Incomplete response/MR/SD	No	PR
PR.	Non-PD	No	PR.
MR	Non-PD	No	MR
SD	Non-PD	No	SD
PD	Any	Yes or no	PD
	PD	Yes or no	PD
Any Any	Any	Yes	PD + 1.1a disease

^{*}CR= complete response; PR= partial response; MR= minor response; SD= stable disease; and PD= progressive disease.

9.2 Toxicity Assessment: This will be performed at intervals defined in section 7.0 using criteria defined in appendices A, B, & C.

10.0 Criteria for Discontinuing Therapy:

- 10.1 Progressive Disease is an indication to discontinue therapy.
- Adverse event(s) that, in the judgment of the Investigator, may cause severe or permanent harm or which rule out continuation of the study drug.
- 10.3 Non-compliance by the patient with protocol requirements.
- 10.4 Patient desire to discontinue therapy.
- 10.5 Evidence of pregnancy.

- 10.6 ... Withdrawal of consent.
- 10.7 Lost to follow-up.
- 10.8 Death

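### A patient whose tumour growth slows by more than 0% but less than 50% must stop drug under 5.2.2, 9.1.5 and 10.1 but continues under the abstract's Treatment Plan; the size criterion for progression also differs between 1.9.5 and 9.1.5

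*Combined protocol and SAP*

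**What the plan says.** **Classification.** Sections 1.9.5 (abstract) and 9.1.5 (body) share two criteria for progressive disease (PD): slowing of growth by less than 50% against the pre-study year, and new metastases. They differ on the third, size. Section 9.1.5 reads "Less than a 50% reduction in the rate of progression (see 9.1.3), an increase of >20% in the size of target lesions"; section 1.9.5 has "an increase of >25% in the size of any measured lesion". Slowing of 50% or more is minor response (MR) in 1.9.3 and 9.1.3, measured on either a linear or a logarithmic volume slope.

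**Stopping.** Section 5.2.2 gives drug "as long as there is no evidence of disease progression (as defined in section 9.0 Response Criteria"). Section 10.1 makes PD an indication to stop. Section 1.8.1 says: "Each patient will continue on study for 12 28-day cycles or until there is evidence of disease progression".

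**Continuing.** The abstract's Treatment Plan carries treatment "past each response assessment point (starting with the second 28-day cycle"), and does so "as long as there is no evidence of disease progression at an equal or greater rate than documented for the baseline year" before treatment. It mentions neither the 50% threshold, nor a size criterion, nor new lesions.

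**Entry.** Inclusion criterion 4 in 5.1.1 requires two scans "demonstrating a cumulative 30% increase in tumor volume over a time period of one year or less". This sets the slowest pre-study growth rate that an eligible patient can have.

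**The concern.** There are two separate problems.

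1. The PD definition stops drug when slowing is below 50%. The Treatment Plan stops it only when there is no slowing at all. Patients in between receive opposite instructions, and no clause says which passage prevails. Preferring the body to the abstract would not clear it up, because 1.8.1 and 1.9.5 are in the abstract too. The PD classification is the same in both sections; the conflict is over what follows from it.

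2. The two size criteria differ in threshold (25% against 20%) and in lesion basis. Section 1.9.5 applies to any single lesion, while 9.1.5 does not say whether target lesions are taken singly or summed. Neither states diameter or volume, or the reference scan. Stable disease in 9.1.4 refers to 9.1.2 for its calculation, and section 6.2 says "A baseline radiological evaluation of tumor volume must be obtained within one week prior to initiating REVLIMID", but the PD size criterion cites neither.

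At stake are time on study drug and the date of PD. That date feeds response duration, a primary objective, if PD is the event that ends a response. The documents do not define that event.

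**Working it through.** The plan gives no figure of its own to reproduce, so the check compares the rules and then sizes the gap.

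**Inputs.** Pre-study growth of 30% in one year (5.1.1, criterion 4), shown as 100 to 130 mL. The 50% threshold (9.1.3, 9.1.5). Scans every two 28-day cycles (7.1), so days 56, 112, 168, … 336. Year = 365.25 days, so day 168 = 0.460 yr and day 336 = 0.920 yr.

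**Part 1: stop or continue.** Let *s* be the percentage slowing against the pre-study year, with no other PD criterion met.

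| Slowing | 9.1.5 with 5.2.2 and 10.1 | Treatment Plan |
|---|---|---|
| *s* ≤ 0 | PD, stop | not continued |
| 0 < *s* < 50 | PD, stop | continue |
| *s* ≥ 50 | MR, continue | continue |

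The middle row at the entry minimum:

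- Linear slope: 30/2 = 15, so growth above 15 and below 30 mL/yr.
- Log slope: exp(ln 1.3 / 2) − 1 = 14.0%, so growth above 14.0% and below 30% a year.

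Example: 30% a year before study, 20% a year on drug.

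- Log slowing: 1 − ln 1.2 / ln 1.3 = 30.5%.
- Linear slowing, starting from 130 mL: 24.0 mL/yr by day 56, so 1 − 24.0/30 = 19.9% before rounding the slope; 25.8 mL/yr by day 336, so 14.0%.
- Volume at day 336: 1.2^0.920 − 1 = +18.3%, below both 20% and 25% if size means volume.

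This patient is PD on either slope in both sections, yet the Treatment Plan allows drug to cycle 12. The gap depends on when the rate can first be judged. The last column is growth at exactly 50% log slowing, exp((ln 1.3 / 2) × d/365.25) − 1.

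| PD called at | Days to day 336 | Growth at 20%/yr | Growth at 50% slowing |
|---|---|---|---|
| day 56 | 280 | 2.8% | 2.0% |
| day 112 | 224 | 5.7% | 4.1% |
| day 168 | 168 | 8.7% | 6.2% |

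The documents give no measurement error, so whether 2.8% can be told from 2.0% at day 56 is not known.

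**Part 2: size criterion.** It matters only when the shared rate criterion is not already met. Assume size is volume, target lesions are summed, and one of five equal lesions grows linearly while the others do not change. Take that lesion at +26% on day 168.

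- Sum: 26/5 = +5.2%.
- Log slowing: 1 − (ln 1.052 / 0.460) / ln 1.3 = 58.0%.
- Linear slowing: 1.3 × 5.2 = 6.76 mL, so 1 − (6.76/0.460)/30 = 51.0%.

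That is PD under 1.9.5 and MR under 9.1.5. On days 56 and 112 it is MR under both (lesion +8.7% and +17.3%; slowing 57.3% and 57.6% log, 51.0% linear). At day 336 the lesion is +52% and the sum +10.4%, with slowing of 59.0% log and 51.0% linear: still not PD under 9.1.5. The PD dates differ by at least 336 − 168 = 168 days.

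Other readings:

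- *Per lesion, volume.* At +26% both sections give PD. At +22% in one of five lesions on day 168, the sum is +4.4% and slowing 64.3% log, 58.5% linear, so it is PD under 9.1.5 only.
- *Four lesions.* +26% in one gives a sum of +6.5% and slowing of 47.8% log, 38.8% linear: PD under both on rate.
- *Diameter, five lesions.* If shape is kept, +26% and +52% in volume are +8.0% and +15.0% in diameter, below both thresholds. Reaching +25% in diameter needs 1.25³ − 1 = +95% in volume. The sum is then +19%, and slowing at day 336 is 28% log, 10% linear: PD under both on rate.
- *Diameter, ten lesions.* The same +95% gives a sum of +9.5% and slowing at day 336 of 62% log, 55% linear. The rate criterion is cleared, so the size criteria can disagree again.
- *Thresholds alone.* Suppose every lesion is +22% at day 336. Clearing the rate criterion on the log slope needs prior growth of at least exp(2 ln 1.22 / 0.920) − 1 = 54% a year. On the linear slope it needs 2 × 0.22/0.920 = 47.8% of baseline-scan volume a year, that is 1/(1 − 0.478) − 1 = 92% a year. Criterion 4 sets no upper limit.

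**The case against.** On part 1, the Treatment Plan sentence stands alone against 1.8.1, 1.9.5, 5.2.2, 9.1.5 and 10.1. Because it leaves out new lesions and size, it can be read as a loose summary. Section 10.1 also says only that PD is an indication to stop. This is fair as to how the conflict may have arisen, but it does not remove it: the sentence states a rule for continuing drug in terms of rate, and 5.2.2 ties drug to section 9.0 without qualification. The 280-day figure is an upper bound.

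On part 2, the 168-day figure rests on chosen assumptions: volume, summed targets and five lesions. With four lesions, or with diameter and five lesions, the sections agree, and the threshold gap alone needs fast prior growth. This stands, and it limits the 168 days to an illustration. It does not dispose of the mismatch, because the ten-lesion diameter case and the +22% per-lesion case also let the sections disagree. The consequences are narrower too: best response is MR under both sections in the five-lesion example, and no effect on the four-cycle count of stage-one responders is claimed.

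**Conclusion.** Both parts hold, and the text must be corrected.

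Part 1 carries the weight. It needs no assumption beyond the wording: every patient with slowing above 0% and below 50%, and no other PD criterion met, has contradictory instructions. The difference in time on drug is 168 to 280 days in the example, according to whether PD is called at day 168 or as early as day 56.

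Part 2 is a real difference in threshold and lesion basis, with a narrower effect that depends on the reading. It can move the PD date, by at least 168 days under the stated five-lesion assumptions, and through that date response duration if PD is the end event.

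**What to change.** Reconcile the abstract's Treatment Plan, 1.8.1, 1.9.5, 5.2.2, 9.1.5 and 10.1 so that one PD definition and one continuation rule apply throughout. The definition should state one threshold, whether lesions are judged singly or summed, diameter or volume, and the reference scan. Use the same definition for best response and response duration. Which threshold and which continuation rule stand is for the sponsor to decide; none is proposed here. The cost is a wording amendment, with no extra patients or procedures.
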